## STUDY SYNOPSIS

**Protocol Title:** A Randomized, Double-blind, Placebo-controlled Parallel Group Phase 2a Study to Evaluate the Efficacy and Safety of HPG1860 in Subjects with Nonalcoholic Steatohepatitis

**Study Number:** HPG1860-201

**Study Name:** Rise

**Clinical Phase:** 2A

**Investigators/Study Centers:** This study will be conducted at approximately 20 study centers, with approximately 20 investigators, located in the United States. Worldwide Clinical Trials, a contract research organization, will oversee operational aspects of this study on behalf of Hepagene (Shanghai) Co., Ltd., the Sponsor of the study.

### Primary Objectives and Endpoints

Objective	Endpoint

To investigate the safety and tolerability profile of HPG1860 3 mg, 5 mg, and 8 mg versus placebo in subjects with nonalcoholic steatohepatitis (NASH).

	
Primary Safety Endpoint
 
Safety and tolerability of 12 -week treatment of HPG1860 3 mg, 5 mg, and 8 mg in subjects with NASH as assessed by:
 

Treatment-emergent adverse events (TEAEs)

Adverse events of special interest (AESI)

Serious adverse events (SAEs)

Changes in clinical safety laboratory values

Vital signs

Electrocardiogram (ECG)

To evaluate the efficacy of HPG1860 compared to placebo.

	
Key Secondary Efficacy Endpoint
 

Change from baseline (CFB) in liver fat content (LFC) measured by magnetic resonance

### Secondary Objectives and Endpoints

	
imaging-proton density fat fraction (MRI-PDFF) at Week 12
 
Other Secondary Endpoints:
 
 
Percentage of subjects with <math>\geq 30\%</math> reduction in LFC from baseline measured by MRI-PDFF at Week 4 and Week 12
 
CFB in LFC as measured by MRI-PDFF at Week 4
 

 
To evaluate the pharmacokinetic (PK) profile of HPG1860 in NASH patients
 
	
PK Endpoints including:
 
 
Area under the curve from time zero to infinity (<math>AUC_{0-\infty}</math>), AUC from time zero to the time of the last quantifiable concentration (<math>AUC_{0-t}</math>), AUC during the 24- hour dosing interval (<math>AUC_{0-24h}</math>), maximum observed concentration (<math>C_{max}</math>), time to maximum plasma concentration (<math>T_{max}</math>), half-life (<math>T_{1/2}</math>), apparent total clearance of the drug from plasma after oral administration (CL/F), and apparent volume of distribution during terminal phase after extravascular administration (<math>V_z/F</math>)
 
Trough concentration (<math>C_{trough}</math>)
 
Accumulation ratio (<math>R_{ac}</math>) based on <math>C_{max}</math> and AUC
 

 
To evaluate the effect of HPG1860 compared to placebo on biomarkers of interest
 
	
 
CFB in insulin, fasting plasma glucose (FPG) and homeostatic model assessment of insulin resistance (HOMA-IR) at Weeks 8, 12, and 16. Note:
 

	
FPG and insulin will be measured as clinical safety laboratory assessments
 
 
• CFB in alanine aminotransferase (ALT), aspartate aminotransferase (AST), gamma-glutamyl transferase (GGT) at Weeks 12 and 16. Note: ALT, AST, and GGT will be measured as clinical safety laboratory assessments
 
• CFB in non-invasive biomarkers of liver injury and apoptosis: cytokeratin-18 (CK-18; M30 and M65 fractions), fibrosis-4 (FIB-4), AST to platelet ratio index (APRI), and N-terminal propeptide of type III collagen (Pro-C3) at Weeks 12 and 16
 
• CFB in enhanced liver fibrosis (ELF), a non-invasive biomarker of fibrosis, hyaluronic acid, procollagen III N-terminal peptide (PIIINP) and tissue inhibitor of metalloproteinase-1 (TIMP-1) at Weeks 12 and 16
 
• CFB in pharmacodynamic (PD) and cardiometabolic biomarkers: high-sensitivity C reactive protein (hs-CRP), 7<math>\alpha</math>-hydroxy-4-cholesten-3-one (C4), alkaline phosphatase (ALP), total bile acids (BAs), non-high density lipoprotein cholesterol (non-HDL-C), low-density lipoprotein cholesterol (LDL-C), total
 

--	--

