- Phenotypic diagnosis based on the following: liver stiffness  $\geq 8.0 \text{ kPa}$  and controlled attenuation parameter (CAP)  $> 300 \text{ dB/m}$  on transient elastography (TE) OR

- Elevated ALT (males >40 IU/L, females >30 IU/L), BMI  $\geq 27$  kg/m^2, and diagnosis of type 2 diabetes mellitus (T2DM).
7. Subjects will have CAP >300 dB/m on TE at screening and hepatic fat assessed by a central reader of MRI-PDFF  $\geq 10\%$  during Screening.
  8. Male subjects must refrain from sperm donation from Screening through at least 90 days following the last dose of IMPs.
  9. Female subjects must refrain from egg donation or harvest for 30 days after last dose of IMPs.
  10. Willing and able to adhere to study restrictions and agree to comply with study protocol.

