**Exclusion Criteria:**

1. Pregnant or lactating females; lactating females must agree to discontinue nursing before the IMPs are administered. WOCBP must have a negative pregnancy test at Screening and Day 1.
2. Past 2 years history of alcohol abuse or current significant alcohol consumption ( >7 drinks per week for males or female; 1 drink = 12 ounces of beer (5% alcohol); 5 ounces of wine (12% alcohol), and 1.5 ounces of 80 proof distilled spirits (40% alcohol) ).
3. LDL-C  $\geq 190$  mg/dL and already on a stable dose of statin and/or proprotein convertase subtilisin/kexin type 9 (PCSK9) inhibitor for  $\geq 30$  days at Screening.
4. Renal dysfunction or nephritic syndrome or a history of nephritis or chronic kidney disease, including estimated glomerular filtration rate (eGFR) (using central laboratory determined Chronic Kidney Disease Epidemiology Collaboration [CKD-EPI] equation) <60 mL/min/1.73 m^2 at Screening.
5. Recent (within 6 months prior to Screening or between Screening and Randomization) myocardial infarction (MI), unstable angina leading to hospitalization, uncontrolled, symptomatic cardiac arrhythmia (or medication for an arrhythmia that was started or dose changed within 3 months of Screening), coronary artery bypass graft surgery (CABG), percutaneous coronary intervention (PCI), carotid surgery or stenting, cerebrovascular accident, transient ischemic attack (TIA), endovascular procedure or surgical intervention for peripheral vascular disease, or plans to undergo a major surgical or interventional procedure (e.g., PCI, CABG, carotid or peripheral revascularization). Subjects with

implantable pacemakers or automatic implantable cardioverter defibrillators may not be considered.

6. Uncontrolled hypertension, defined as sitting systolic blood pressure (SBP)  $\geq 160$  mmHg and/or diastolic blood pressure (DBP)  $\geq 100$  mmHg after sitting quietly for 5 minutes at Screening.
7. Type 1 diabetes or uncontrolled T2DM including  $HbA_{1c} \geq 9.5\%$  at Screening.
8. Uncontrolled hypothyroidism, including thyroid stimulating hormone (TSH)  $> 1.5 \times$  the upper limit of normal (ULN) at Screening.
9. Liver transplant and/or other significant liver disease or dysfunction including:
  - a. History of hepatic decompensation (such as ascites, variceal hemorrhage, hepatic encephalopathy, jaundice, and hepatorenal syndrome).

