17. History within the last 2 years of drug abuse including but not limited to, amphetamine and derivatives, or cocaine. Subjects with amphetamine derivatives prescribed by and under the care of a health care practitioner can be enrolled after evaluation by the investigator.
18. Blood donation, blood transfusion, participation in a clinical study with multiple blood draws, major trauma, or surgery with or without blood loss within 30 days prior to randomization and throughout the duration of study participation.
19. Use of any experimental or investigational drugs within 30 days prior to Screening.
20. Use of any of the following prior to Screening unless otherwise stated or a plan to use these drugs during the study is **prohibited**:
  - a. High-dose vitamin E ( $>400$  IU/day) (1 month prior to Screening).
  - b. Pioglitazone (3 months prior to Screening).
  - c. Medications associated with increased hepatic steatosis including mipomersen, lomitapide, amiodarone, methotrexate, tamoxifen, antiretrovirals, oral glucocorticoids at doses  $\geq 5$  mg

per day and/or valproic acid (3 months prior to Screening).

- d. Substrates for P-glycoprotein (P-gp) and/or breast cancer resistance protein (BCRP) including rosuvastatin (1 month prior to Screening) (Appendix 13).
21. Starting or adjusting the dose of the following permitted drugs within 5 weeks prior to Screening. These drugs are **allowed as long as stable** at least 5 weeks prior to Screening unless otherwise noted:
- a. Lipid regulating medications (except for rosuvastatin, which is prohibited) may be included; however, those that may affect liver steatosis or may have a potential drug-drug interaction risk are excluded per principal investigator (PI) discretion.
  - b. Hormone replacement.
  - c. Thyroid replacement.
  - d. Obesity medication (if dose is stable 6 months prior to Screening).
  - e. Diabetes medications (if dose is stable 3 months prior to Screening).
22. Unable to undergo or contraindication to MRI procedure (i.e., extensive tattoos, pacemaker, shrapnel injury, severe claustrophobia, ear (cochlea) implant).
23. History of intestinal resection or malabsorptive condition that may limit the absorption of HPG1860.
24. A medical or situational (i.e., geographical) finding that in the investigator's opinion may compromise the subject's safety or ability to complete the study.

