#### **Analysis Populations**

The Intent-to-Treat (ITT) Population, used for all of the efficacy analyses, is defined as all randomized subjects. Subjects will be reported according to randomized study treatment.

The Per-Protocol (PP) Population, used for sensitivity analyses on the primary endpoint, is defined as all randomized subjects who received at least 80 to 120% of randomized treatment and had no major protocol deviations. Subjects will be reported according to randomized study treatment.

The Safety Population (SP), used for all of the safety summaries, is defined as all randomized subjects who received at least 1 dose of blinded IMP. Subjects will be reported according to actual treatment received at the first dose.

The PK Analysis Set (PKS), used for all of the PK-related summaries, is defined as all subjects in the SP who have at least 1 resulted PK assessment. Subjects will be reported according to actual treatment received at the first dose.

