### **Other Secondary Efficacy, Pharmacokinetic, and Pharmacodynamic Analyses**

The proportion of subjects with  $\geq 30\%$  reduction in LFC from baseline to Week 4 and Week 12 will separately be compared across treatment groups using a chi-square test.

The change in LFC measured by MRI-PDFF from baseline to Week 4 will be compared using ANCOVA as proposed for the primary efficacy analysis.

PK parameters including  $AUC_{0-\infty}$ ,  $AUC_{0-t}$ ,  $AUC_{0-24h}$ ,  $C_{max}$ ,  $T_{max}$ ,  $T_{1/2}$ ,  $CL/F$ ,  $V_z/F$ ,  $R_{ac}$ , and  $C_{trough}$  of HPG1860 in subjects with NASH will be reported by dose group and study day.

Biomarkers for liver injury and apoptosis, fibrosis, metabolism/cardiometabolic, and other biomarkers will be summarized by the value and by CFB in the value (where appropriate) at each postbaseline time point.

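### Insulin-treated type 2 diabetics are eligible, yet change in insulin and HOMA-IR is summarised with no restriction or split by insulin use

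*Combined protocol and SAP*

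**What the plan says.** All references are to the combined protocol and SAP.

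- **Endpoint.** Secondary Objectives and Endpoints lists "CFB in insulin, fasting plasma glucose (FPG) and homeostatic model assessment of insulin resistance (HOMA-IR) at Weeks 8, 12, and 16", under the objective of comparing biomarkers of interest between HPG1860 and placebo. A note adds that "FPG and insulin will be measured as clinical safety laboratory assessments". No assay is described and C-peptide is not mentioned.
- **Route into the trial.** Under Inclusion Criteria, item 6, one of three ways to qualify as NASH combines raised ALT, BMI of at least 27 kg/m² and a "diagnosis of type 2 diabetes mellitus (T2DM)".
- **Diabetes exclusion.** Exclusion criterion 7 removes "Type 1 diabetes or uncontrolled T2DM including" HbA1c of 9.5% or more. Insulin treatment is not mentioned.
- **Diabetes medication.** Exclusion criterion 21e allows "Diabetes medications (if dose is stable 3 months prior to Screening)". The only glucose-lowering drug on the prohibited list is at 20b: "Pioglitazone (3 months prior to Screening)".
- **Analysis.** Other Secondary Efficacy, Pharmacokinetic, and Pharmacodynamic Analyses says that biomarkers "will be summarized by the value and by CFB in the value (where appropriate) at each postbaseline time point". It gives no restriction or split by insulin use.
- **Population.** Analysis Populations describes the ITT Population as "used for all of the efficacy analyses, is defined as all randomized subjects". It does not name a population for biomarkers.

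**The concern.** HOMA-IR combines glucose and insulin, and is read as an index of resistance on the understanding that the insulin is the subject's own. That fails in a subject who injects insulin. If the assay detects the injected product, the result moves with dose and with time since injection. If it does not, the subject's own secretion has still been altered by treatment.

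The eligibility rules admit such subjects and the biomarker summary does not separate them. With about 20 subjects per arm, one or two erratic values can widen the spread of an arm or shift its mean. At stake is whether a named secondary biomarker comparison with placebo can be read: a metabolic effect could be obscured, or an apparent one could come from an uneven spread of insulin users.

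**Working it through.** **1. The plan's own figure.** None is stated for insulin or HOMA-IR. The only power figure concerns liver fat content (LFC): 17 per group, difference 7.0, SD 6.8, Dunnett's test, two-sided 0.05, 90% power. Simulation with 400,000 runs gives 90.8% power for at least one dose to differ from placebo when all three doses have the 7.0 effect, and 17/(1 − 0.15) = 20 per group. That figure is reproduced, and this point does not touch it.

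**2. Eligibility.** Type 2 diabetes is an entry route, exclusion is limited to type 1 or uncontrolled disease, and stable diabetes medication is allowed as a class. Where the authors wanted an exception they wrote one: pioglitazone at 20b and rosuvastatin at 21a. There is none for insulin. A type 2 diabetic on a stable insulin dose is therefore eligible. This is inferred from the class permission, since the text names insulin only as a laboratory measure.

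**3. What change from baseline removes.** Assume HOMA-IR is proportional to G × I (glucose times measured insulin; the formula is not in the documents). Write I = E + cX, where E is own insulin, X is circulating injected insulin and c is the fraction the assay detects.

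- Change in insulin = (E_t − E_0) + c(X_t − X_0). If X is the same at both visits, the injected part cancels.
- Change in G × I with constant X = (G_t·E_t − G_0·E_0) + cX(G_t − G_0). The injected part cancels only to the extent that glucose is unchanged.
- If X differs between visits through timing or dose, neither change is clean. The 3-month stability rule in 21e applies before Screening.

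For scale, with assumed own insulin of 20 and detected injected insulin of 20 or 60 (same units), HOMA-IR at a given glucose is multiplied by (20 + 20)/20 = 2 or (20 + 60)/20 = 4.

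**4. Noise in an arm mean.** Let p be the share of insulin users and k the ratio of their SD of change to that of the others. Both are assumed, and mean change is taken as equal in the two sets. Relative to an arm of 20 with no users:

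- all subjects pooled: variance factor 1 + p(k² − 1)
- non-users only: variance factor 1/(1 − p)

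| p | k | pooled | non-users only |
|---|---|---|---|
| 0.05 | 2 | 1 + 0.05 × 3 = 1.15 | 1/0.95 = 1.05 |
| 0.10 | 3 | 1 + 0.10 × 8 = 1.8 | 1/0.90 = 1.11 |
| 0.20 | 5 | 1 + 0.20 × 24 = 5.8 | 1/0.80 = 1.25 |

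In the middle row, pooling leaves 20/1.8 = 11.1 effective subjects against 18 non-users. Restriction is the more precise choice when k² > 1 + 1/(1 − p), that is, k above about 1.43 at p = 0.05 and above 1.5 at p = 0.20.

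**5. Chance imbalance.** With 20 subjects in each of two arms and users distributed binomially, the simulated probability that the arms differ by two or more users is 25% at p = 0.05, 42% at 0.10, 55% at 0.20 and 60% at 0.30 (all assumed shares).

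**The case against.** The strongest reply has five parts.

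- **Population.** A reader might infer that the plan commits HOMA-IR to an analysis of all randomized subjects. The text does not go that far. ITT is assigned to efficacy analyses, the objectives list biomarkers separately from efficacy, and insulin and FPG are described as safety laboratory measures. What stands is narrower: whichever population is used, nothing separates insulin users. The qualifier on reporting change where appropriate does not identify any subjects to leave out.
- **Mechanism.** A reader might also infer that injected insulin will be counted as insulin resistance, or that HOMA-IR change in these subjects measures only injection timing and dose. Detection depends on an assay that is not described, and a stable contribution partly cancels. The supportable claim is that the change is hard to interpret.
- **Direction.** Allocation is randomized 1:1:1:1 and double-blind, so no systematic bias between arms is shown. The exposure is to added variance and chance imbalance.
- **Size.** Every magnitude here is assumed, and a range from 1.15 to 5.8 runs from trivial to large. This stands in full.
- **Completeness.** The text available is at synopsis level and points to an appendix, so handling rules could exist elsewhere. This also stands: the point applies to the text as given.

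One further caution concerns the remedy. Dropping subjects who start insulin during the study would condition on a post-randomization event that may be related to treatment, and could replace noise with selection bias. The restriction should therefore use baseline status only.

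**Conclusion.** The point holds in limited form. Eligibility admits insulin-treated subjects, and the biomarker summary mixes their insulin and HOMA-IR changes with those of subjects for whom the index has its usual meaning. The consequence is a noisier and less interpretable descriptive comparison in arms of about 20.

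Its size cannot be derived from the documents. The illustrative factors (1.15 to 5.8 for the variance of an arm mean) rest on an assumed user share of 5–20%, an assumed SD ratio of 2–5 and equal mean change. The conclusion also presumes that some insulin users enrol.

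This is a minor, worthwhile improvement. The plan states no hypothesis test or decision rule for these biomarkers, and the LFC analysis, the sample size and the primary safety assessment are unaffected.

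**What to change.** In Other Secondary Efficacy, Pharmacokinetic, and Pharmacodynamic Analyses, add a rule for insulin and HOMA-IR only:

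- The main summary of value and change covers subjects not receiving exogenous insulin at baseline.
- The number omitted for this reason is shown for each arm.
- The same summary in all subjects is given as a sensitivity summary.
- Subjects who start insulin after randomization stay in the main summary and are flagged, with counts per arm.
- FPG is summarised in all subjects.

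Name the analysis population for biomarkers in the same place. Eligibility and treatment are unchanged.

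The cost is a sentence or two in the SAP, a concomitant-medication flag and one extra table. The main summary of these two biomarkers loses a few subjects: under the assumed 5–20% share, 20 × 0.05 = 1 to 20 × 0.20 = 4 of 20 per arm.

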**Exploratory Objectives and Endpoints**

	cholesterol (TC), and apolipoprotein B (apoB) at Weeks 2, 4, 8, 12, and 16. Note: HDL-C, LDL-C, and triglycerides (TG) will be measured as clinical safety laboratory assessments

 
To collect reserve samples for future evaluation of the effect of HPG1860 compared to placebo on additional biomarkers, not otherwise described
 
To characterize HPG1860 metabolites
 
To characterize the relationship between PK values and study outcomes
 
	
 
Assess biomarkers, not otherwise described, acquired from reserve samples
 
To measure HPG1860 metabolites
 
Explore correlations between PK concentration and LFC
 

**Other Safety Measures:**

- Physical examination (PE)
- Weight

**Study Design:**

This is a Phase 2a, randomized, double-blind, placebo-controlled, parallel group, multiple arm, multicenter study of 3 different doses of HPG1860 versus placebo in subjects with biopsy-confirmed or phenotypic NASH. Screening will occur up to 5 weeks prior to randomization; all eligible subjects will have baseline hepatic imaging during Screening, prior to randomization. Approximately 80 eligible subjects will be randomized 1:1:1:1 on Day 1/Week 0 (T1) to receive either HPG1860 3 mg (n = 20), or 5 mg (n = 20), or 8 mg (n = 20), or placebo (n = 20) for 12 weeks. Following a preplanned interim analysis, a dose cohort may be dropped and/or added.

Randomized subjects will return for clinic visits at Week 2 (T2), Week 4 (T3), Week 8 (T4), and Week 12 (T5) as well as Week 16 (T6). Imaging procedures will be completed during Screening, Week 4 (T3), and Week 12 (T5). A follow-up visit will be completed 4 weeks after last dose of investigational medicinal product (IMP) at Week 16 (Visit T6).

At selected PK sites, serial PK samples will be collected from approximately 6 to 8 subjects in each dose cohort; blood samples will be collected on Day 1 pre-dose (within 30 minutes prior to dosing) and at 1, 2, 4, 6, and 8 hours ( $\pm 15$  minutes) post-dosing and on Day 14 pre-dose (within 30 minutes before dosing) and at 1, 2, 4, 6, and 8 hours ( $\pm 15$  minutes) post-dosing, and at 24 hours

(±30 minutes) prior to dosing on Day 15.

For all subjects, PK samples will be taken within 30 minutes prior to dosing at Weeks 4, 8, 12, and 16.

This study includes collection of reserve samples at Baseline (Day 1) and Week 12 for future biomarker analysis, unless prohibited by local law or regulations, and where approved by the Institutional Review Board (IRB).

**Duration of  
Treatment:**

Total study duration per subject: 21 weeks (approximate)

Screening: up to 5 weeks

Treatment: 12 weeks

Follow-up: 4 weeks

**Planned Sample Size  
and Treatment  
Groups:**

Planned: Approximately 80 adult male and female subjects

HPG1860 3 mg (n=20)

HPG1860 5 mg (n = 20)

HPG1860 8 mg (n = 20)

Placebo (n = 20)

Following a preplanned unblinded (comparative) interim analysis when 50% of randomized subjects have reached the Week 12 endpoint, an ongoing treatment group (3 mg, 5 mg, or 8 mg) may be dropped and/or a new treatment group of dose may be added.

**Target Population:**

Subjects with biopsy-confirmed or phenotypic NASH.

**Eligibility Criteria:**

**Inclusion Criteria:**

1. Provision of written informed consent prior to any study-specific procedure.
2. Males and females between 18 and 75 years of age; inclusive based on the date of Screening.
3. Nonpregnant, nonlactating women. Women must be either:
  - a. Females who are postmenopausal must have cessation of menses for at least 12 months without an alternative medical cause and with screening FSH≥40, or.

Note: females on hormone replacement therapy (HRT) and whose menopause status is in doubt will be required to use contraception methods described in exclusive criteria if they wish to continue their HRT during the study. Otherwise, they must temporarily stop HRT to enable confirmation of post

menopausal status before study enrollment.

- b. Surgically sterile prior to Screening including hysterectomy, bilateral oophorectomy, or tubal ligation, or
- c. Women of childbearing potential (WOCBP) willing to use at least 1 acceptable method of birth control. The minimal requirement for adequate contraception should be functional on Day 1, continuing during the study period and for at least 30 days after the last dose of IMP. Acceptable methods of birth control include:
  - i. Oral, implantable, injectable, or topical birth control medications.
  - ii. Placement of an intrauterine device with or without hormones.
  - iii. Barrier methods including condom or occlusive cap with spermicidal foam or spermicidal jelly.
  - iv. Vasectomized male partner who is the sole partner for this subject.
  - v. True abstinence, when this is in line with the preferred and usual lifestyle of the subject. (Periodic abstinence [e.g., calendar, ovulation, symptothermal, postovulation methods], declaration of abstinence for the duration of a trial, and withdrawal are not acceptable methods of contraception).
4. Male subjects must agree to utilize a highly effective method of contraception (condom) during heterosexual intercourse from the Screening through the study completion and for 90 days following the last dose of IMPs.
5. Body mass index (BMI) of  $\geq 25 \text{ kg/m}^2$  (per MRI feasibility) at Screening.
6. Non-cirrhotic NASH subjects.

Presence of NASH is defined as at least 1 of the following at screening:

- Biopsy-confirmed NASH and F1-F3 fibrosis (Clinical Research Network [CRN]), historical data of biopsy procedure obtained 24 months prior to randomization can be used OR
- Phenotypic diagnosis based on the following: liver stiffness  $\geq 8.0 \text{ kPa}$  and controlled attenuation parameter (CAP)  $> 300 \text{ dB/m}$  on transient elastography (TE) OR

- Elevated ALT (males >40 IU/L, females >30 IU/L), BMI  $\geq 27$  kg/m^2, and diagnosis of type 2 diabetes mellitus (T2DM).
7. Subjects will have CAP >300 dB/m on TE at screening and hepatic fat assessed by a central reader of MRI-PDFF  $\geq 10\%$  during Screening.
  8. Male subjects must refrain from sperm donation from Screening through at least 90 days following the last dose of IMPs.
  9. Female subjects must refrain from egg donation or harvest for 30 days after last dose of IMPs.
  10. Willing and able to adhere to study restrictions and agree to comply with study protocol.

